11.6 ROUTINE ADVERSE EVENT REPORTING

For non-serious Adverse Events, documentation must begin from the time the informed consent document is signed through the 30-day follow-up period after study drug is discontinued.

Collected information should be recorded in the electronic/Case Report Forms (eCRF/CRF) for that subject. A description of the event, its severity or toxicity grade (according to [NCI's](#)

Common Toxicity Criteria (CTCAE)4.04), onset and resolved dates (if applicable), and the relationship to the study drug should be included. Documentation should occur in real time. The principal investigator has final responsibility for determining the attribution of the event as it is related to the study drug.

For any experience or condition that meets the definition of a serious adverse event (SAE), recording of the event must begin after signing of the informed consent and continue through the 30-day follow-up period after treatment is discontinued.

Investigators must report to the DSMC any serious adverse events (SAE), whether or not they are considered related to the investigational agent(s)/intervention (21 CFR 312.64). SAEs must be reported via an OnCore SAE Report within 24 hours of learning of the event.

An adverse event is considered **serious** if it results in ANY of the following outcomes:

- Death
- A life-threatening adverse event
- An adverse event that results in inpatient hospitalization OR prolongation of existing hospitalization for ≥ 24 hours
- A persistent or significant incapacity or substantial disruption of the ability to conduct normal life functions
- A congenital anomaly/birth defect.
- Important Medical Events (IME) that may not result in death, be life threatening, or require hospitalization may be considered serious when, based upon medical judgment, they may jeopardize the patient or subject and may require medical or surgical intervention to prevent one of the outcomes listed in this definition. (FDA, [21 CFR 312.32](#); [ICH E2A](#) and [ICH E6](#)).

11.7.1 EXELIXIS REPORTING

As soon as an investigator becomes aware of an AE that meets the definition of ‘serious,’ this must be documented on an SAE Report Form or in an electronic database and include the following: (i) all SAEs that occur after starting cabozantinib and through 30 days after the decision to discontinue study treatment and (ii) any SAEs assessed as related to study treatment or study procedures, from the time of informed consent, even if the SAE occurs more than 30 days after the decision to discontinue study treatment.

All SAEs that are assessed by the PI as **related** to drug or study procedure and all pregnancy/lactation reports regardless of outcome must be sent to Exelixis within one (1) business day of the PI’s knowledge of the event. The reports must be sent to [contact] or [contact].

- The PI will perform adequate due diligence with regard to obtaining follow-up information on incomplete reports. All follow-up information must be sent to Exelixis within one (1) business day of the PI’s receipt of the new information. Upon Exelixis request, the PI will query for follow-up information.

11.7.2 REGULATORY REPORTING

The Investigator will assess the expectedness of each related SAE. The current cabozantinib/pembrolizumab Reference Safety Information (Appendix K of the most recent approved

Investigator Brochure) will be used as the reference document for assessing the expectedness of the event with regard to cabozantinib or pembrolizumab. All serious unexpected adverse drug reactions (unexpected related SAEs) must be reported to all appropriate regulatory authorities and Ethics Committees by the investigator as required by 21 CFR 312.32 or by Directive 2011/20/EC:

- These reports are to be filed utilizing the Form FDA 3500A (MedWatch Form) or a CIOMS-1 form;
- Exelixis reserves the right to upgrade the Investigator assessment of an SAE based on Exelixis assessment.
- Institutions and PIs shall promptly provide all information requested by Exelixis regarding all adverse events occurring during the conduct of the study.
- The PI is responsible for complying with all regulatory authority reporting requirements for the study that are applicable to the sponsor of a clinical trial. The PI shall provide a copy of all responses to regulatory agency requests, periodic reports, and final study reports to Exelixis within one (1) business day of the submission.
- Exelixis will provide relevant product safety updates and notifications, as necessary. In the case of multi-center studies, it is the responsibility of the sponsoring PI/Institution to disseminate these updates to participating PIs.

11.8 DATA MONITORING AND MANAGEMENT

All studies that undergo PRMC review and/or utilize HCCC Clinical Research Services (CRS) resources are required to register subjects in OnCore. Subject registration includes the following:

- Consent date and the IRB approved consent used
- Date of eligibility and eligibility status (eligible, not eligible)
- On study date and subject's disease site (and histology if applicable)
- On treatment date (if applicable)

Subject Data

In addition to the subject registration and subject status data entered in OnCore for all HCCC trials, research staff also enters the subject study data into electronic case report forms (eCRFs) for HCCC investigator initiated studies. eCRFs are approved by the PI and statistician prior to study activation to ensure the most effective data acquisition. All information on eCRFs will be traceable to the source documents which are generally maintained in the subject's file. eCRF data are expected to be entered into OnCore within 30 calendar days after a subject's study visit.

Forms Monitoring

OnCore eCRF data are monitored on a routine basis (dependent on accrual) to ensure all mandatory fields are entered completely, accurately and within time requirements. The assigned DSMC monitor manages the logistics associated with the data monitoring review. Once the clinical trial is identified for monitoring, the monitor arranges for a selection of cases to review from among the subjects registered in OnCore. As part of the forms monitoring process, the assigned monitor will issue queries within the eCRF to resolve missing, incomplete and/or incorrect information. A member of the research team is expected to respond to monitoring queries within 14 business days.

This process can often identify a misunderstanding or deficiency in protocol requirements early in the study and can improve data quality.

Final Reports

A summary of each subject's data record is continually available to the PI, research staff, and DSMC from OnCore's Biostat Console. The availability of this information is a valuable tool for the preparation of final reports and manuscripts as well as ongoing deficiency reports.

11.9 SPECIMEN COLLECTION FOR BIOMARKER TESTING

PHASE II (EXPANSION) ONLY

Archival Tumor Tissue: A sample of archival tumor tissue will be obtained at baseline on all patients enrolled in the expansion portion for biomarker studies, if available.

Blood samples: 5 tubes of blood will be drawn in unheparinized tubes, spun and stored at -80 c for future biomarker studies. Samples will be drawn at the same time as standard of care labs at baseline, week 7 (+/- 1 week) and at time of progression for a select number of patients enrolled in the expansion portion of the study.

Optional Fresh Biopsy: For select patients, tumor tissue samples (fresh) will be obtained at baseline, week 7 (+/- 1 week) and progression for subjects who consented to optional samples at time of consent during the expansion portion of the study and have superficial lesions (skin/lymph nodes). Tissue samples will be flash frozen and stored at -80 C to be processed later for biomarker testing. Recommend: Per PI discretion, Cabozantinib be held for 4 days prior to biopsy and restarted 7 days after biopsy provided adequate wound healing is achieved.

Number of patients: 10-15

Tests: IHC: Angiogenic and Immune markers: Expansion Phase

Timeline:

	Baseline	At 7 weeks +/- 1 week	At progression
Tissue (core biopsy)	X	X	X
Peripheral blood (for biomarker studies)	X	X	X

13. PROTOCOL AMENDMENT HISTORY

Protocol Appendix A- Recist 1.1 Quick Reference

Response Evaluation Criteria in Solid Tumors (RECIST) Quick Reference:

Eligibility

- Only patients with measurable disease at baseline should be included in protocols where objective tumor response is the primary endpoint.

Measurable disease - the presence of at least one measurable lesion. If the measurable disease is restricted to a solitary lesion, its neoplastic nature should be confirmed by cytology/histology.

Measurable lesions - lesions that can be accurately measured in at least one dimension with longest diameter ≥ 20 mm using conventional techniques or ≥ 10 mm with spiral CT scan.

Non-measurable lesions - all other lesions, including small lesions (longest diameter <20 mm with conventional techniques or <10 mm with spiral CT scan), i.e., bone lesions, leptomeningeal disease, ascites, pleural/pericardial effusion, inflammatory breast disease, lymphangitis cutis/pulmonis, cystic lesions, and also abdominal masses that are not confirmed and followed by imaging techniques; and.

- All measurements should be taken and recorded in metric notation, using a ruler or calipers. All baseline evaluations should be performed as closely as possible to the beginning of treatment and never more than 4 weeks before the beginning of the treatment.
- The same method of assessment and the same technique should be used to characterize each identified and reported lesion at baseline and during follow-up.
- Clinical lesions will only be considered measurable when they are superficial (e.g., skin nodules and palpable lymph nodes). For the case of skin lesions, documentation by color photography, including a ruler to estimate the size of the lesion, is recommended.

Methods of Measurement –

- CT and MRI are the best currently available and reproducible methods to measure target lesions selected for response assessment. Conventional CT and MRI should be performed with cuts of 10 mm or less in slice thickness contiguously. Spiral CT should be performed using a 5 mm contiguous reconstruction algorithm. This applies to tumors of the chest, abdomen and pelvis. Head and neck tumors and those of extremities usually require specific protocols.
- Lesions on chest X-ray are acceptable as measurable lesions when they are clearly defined and surrounded by aerated lung. However, CT is preferable.
- When the primary endpoint of the study is objective response evaluation, ultrasound (US) should not be used to measure tumor lesions. It is, however, a possible alternative to clinical measurements of superficial palpable lymph nodes, subcutaneous lesions and thyroid nodules. US might also be useful to confirm the complete disappearance of superficial lesions usually assessed by clinical examination.
- The utilization of endoscopy and laparoscopy for objective tumor evaluation has not yet been fully and widely validated. Their uses in this specific context require sophisticated equipment and a high level of expertise that may only be available in some centers. Therefore, the utilization of such techniques for objective tumor response should be restricted to validation purposes in specialized centers. However, such techniques can be useful in confirming complete pathological response when biopsies are obtained.
- Tumor markers alone cannot be used to assess response. If markers are initially above the upper normal limit, they must normalize for a patient to be considered in complete clinical response when all lesions have disappeared.
- Cytology and histology can be used to differentiate between PR and CR in rare cases (e.g., after treatment to differentiate between residual benign lesions and residual malignant lesions in tumor types such as germ cell tumors).

Baseline documentation of “Target” and “Non-Target” lesions

- All measurable lesions up to a maximum of five lesions per organ and 10 lesions in total, representative of all involved organs should be identified as **target lesions** and recorded and measured at baseline.
- Target lesions should be selected on the basis of their size (lesions with the longest diameter) and their suitability for accurate repeated measurements (either by imaging techniques or clinically).

- A sum of the longest diameter (LD) for *all target lesions* will be calculated and reported as the baseline sum LD. The baseline sum LD will be used as reference by which to characterize the objective tumor.
- All other lesions (or sites of disease) should be identified as ***non-target lesions*** and should also be recorded at baseline. Measurements of these lesions are not required, but the presence or absence of each should be noted throughout follow-up.

Response Criteria

Evaluation of target lesions

* Complete Response (CR):	Disappearance of all target lesions
* Partial Response (PR):	At least a 30% decrease in the sum of the LD of target lesions, taking as reference the baseline sum LD
* Progressive Disease (PD):	At least a 20% increase in the sum of the LD of target lesions, taking as reference the smallest sum LD recorded since the treatment started or the appearance of one or more new lesions
* Stable Disease (SD):	Neither sufficient shrinkage to qualify for PR nor sufficient increase to qualify for PD, taking as reference the smallest sum LD since the treatment started

Evaluation of non-target lesions

* Complete Response (CR):	Disappearance of all non-target lesions and normalization of tumor marker level
* Incomplete Response/ Stable Disease (SD):	Persistence of one or more non-target lesion(s) or/and maintenance of tumor marker level above the normal limits
* Progressive Disease (PD):	Appearance of one or more new lesions and/or unequivocal progression of existing non-target lesions (1)

(1) Although a clear progression of “non target” lesions only is exceptional, in such circumstances, the opinion of the treating physician should prevail and the progression status should be confirmed later on by the review panel (or study chair).

Evaluation of best overall response

The best overall response is the best response recorded from the start of the treatment until disease progression/recurrence (taking as reference for PD the smallest measurements recorded since the treatment started). In general, the patient's best response assignment will depend on the achievement of both measurement and confirmation criteria

Target lesions	Non-Target lesions	New Lesions	Overall response
CR	CR	No	CR
CR	Incomplete response/SD	No	PR
PR	Non-PD	No	PR
SD	Non-PD	No	SD
PD	Any	Yes or No	PD
Any	PD	Yes or No	PD
Any	Any	Yes	PD

- Patients with a global deterioration of health status requiring discontinuation of treatment without objective evidence of disease progression at that time should be classified as having “symptomatic deterioration”. Every effort should be made to document the objective progression even after discontinuation of treatment.
- In some circumstances it may be difficult to distinguish residual disease from normal tissue. When the evaluation of complete response depends on this determination, it is recommended that the residual lesion be investigated (fine needle aspirate/biopsy) to confirm the complete response status.

Confirmation

- The main goal of confirmation of objective response is to avoid overestimating the response rate observed. In cases where confirmation of response is not feasible, it should be made clear when reporting the outcome of such studies that the responses are not confirmed.
- To be assigned a status of PR or CR, changes in tumor measurements must be confirmed by repeat assessments that should be performed no less than 4 weeks after the criteria for response are first met. Longer intervals as determined by the study protocol may also be appropriate.
- In the case of SD, follow-up measurements must have met the SD criteria at least once after study entry at a minimum interval (in general, not less than 6-8 weeks) that is defined in the study protocol

Duration of overall response

- The duration of overall response is measured from the time measurement criteria are met for CR or PR (whichever status is recorded first) until the first date that recurrence or PD is objectively documented, taking as reference for PD the smallest measurements recorded since the treatment started.

Duration of stable disease

- SD is measured from the start of the treatment until the criteria for disease progression are met, taking as reference the smallest measurements recorded since the treatment started.
- The clinical relevance of the duration of SD varies for different tumor types and grades. Therefore, it is highly recommended that the protocol specify the minimal time interval required between two measurements for determination of SD. This time interval should take into account the expected clinical benefit that such a status may bring to the population under study.

Response review

- For trials where the response rate is the primary endpoint it is strongly recommended that all responses be reviewed by an expert(s) independent of the study at the study's completion. Simultaneous review of the patients' files and radiological images is the best approach.

Reporting of results

- All patients included in the study must be assessed for response to treatment, even if there are major protocol treatment deviations or if they are ineligible. Each patient will be assigned one of the following categories: 1) complete response, 2) partial response, 3) stable disease, 4) progressive disease, 5) early death from malignant disease, 6) early death from toxicity, 7) early death because of other cause, or 9) unknown (not assessable, insufficient data).
- All of the patients who met the eligibility criteria should be included in the main analysis of the response rate. Patients in response categories 4-9 should be considered as failing to respond to treatment (disease progression). Thus, an incorrect treatment schedule or drug administration does not result in exclusion from the analysis of the response rate. Precise definitions for categories 4-9 will be protocol specific.
- All conclusions should be based on all eligible patients.
- Subanalyses may then be performed on the basis of a subset of patients, excluding those for whom major protocol deviations have been identified (e.g., early death due to other reasons, early discontinuation of treatment, major protocol violations, etc.). However, these subanalyses may not serve as the basis for drawing conclusions concerning treatment efficacy, and the reasons for excluding patients from the analysis should be clearly reported.
- The 95% confidence intervals should be provided.

Protocol Appendix B- Performance Status Criteria

ECOG Performance Status Scale		Karnofsky Performance Scale	
Grade	Descriptions	Percent	Description
0	Normal activity. Fully active, able to carry on all pre-disease performance without restriction.	100	Normal, no complaints, no evidence of disease.
		90	Able to carry on normal activity; minor signs or symptoms of disease.
1	Symptoms, but ambulatory. Restricted in physically strenuous activity, but ambulatory and able to carry out work of a light or sedentary nature (e.g., light housework, office work).	80	Normal activity with effort; some signs or symptoms of disease.
		70	Cares for self, unable to carry on normal activity or to do active work.
2	In bed <50% of the time. Ambulatory and capable of all self-care, but unable to carry out any work activities. Up and about more than 50% of waking hours.	60	Requires occasional assistance, but is able to care for most of his/her needs.
		50	Requires considerable assistance and frequent medical care.
3	In bed >50% of the time. Capable of only limited self-care, confined to bed or chair more than 50% of waking hours.	40	Disabled, requires special care and assistance.
		30	Severely disabled, hospitalization indicated. Death not imminent.
4	100% bedridden. Completely disabled. Cannot carry on any self-care. Totally confined to bed or chair.	20	Very sick, hospitalization indicated. Death not imminent.
		10	Moribund, fatal processes progressing rapidly.
5	Dead.	0	Dead.

Protocol Appendix C- CABOZANTINIB MEDICATION DIARY

CYCLE NUMBER	
NUMBER OF PILLS DISPENSED	
DAILY DOSE	
NUMBER OF PILLS RETURNED	
NUMBER OF PILLS EXPECTED TO BE TAKEN THIS CYCLE	
ACTUAL NUMBER OF PILLS TAKEN THIS CYCLE	
EXPLANATION FOR DISCREPANCY IN COUNT	

PILL COUNT TO BE COMPLETED BY RESEARCH COORDINATOR

PLEASE FILL OUT AND BRING THIS SHEET TO ALL VISITS.

SPECIAL INSTRUCTIONS:

1. Cabozantinib should be taken orally without food. Do not eat from atleast 2 hours before through 1 hour after each dose of cabozantinib.
2. Cabozantinib should be taken at approximately the same time every day. If a dose is missed, please take the dose as soon as possible, but only if there are 12 or more hours remaining before the next dose
 - a. If the dose is due in less than 12 hours, skip the missed dose and take the next dose as scheduled
 - b. Remember to record missed doses
3. If vomiting occurs after taking cabozantinib, do not take a replacement dose on that day. Resume at the next scheduled dose
 - a. If it appears that an intact tablet has been expelled do not take a replacement dose that day
 - b. If consistent vomiting occurs please notify the study investigator
4. Cabozantinib tablets should be swallowed whole with at least 8 ounces of water. The tablets should not be crushed. Grapefruit, grapefruit juice, Seville oranges and their products should be avoided while taking Cabozantinib.
5. Cabozantinib tablets should be stored at room temperature.

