Randomization was stratified by line of therapy (0 vs. 1), ECOG PS (0 vs. 1), and PD-L1 expression ($\geq 1\%$ of tumor cells [positive] vs. $< 1\%$ of tumor cells [negative]) according to an investigational use only (IUO) assay. Key eligibility criteria were unresectable or metastatic melanoma; no prior ipilimumab; and no more than one prior systemic treatment for metastatic melanoma. Subjects with BRAF V600E mutation-positive melanoma were not required to have received prior BRAF inhibitor therapy. Patients with autoimmune disease; a medical condition that required immunosuppression; previous severe hypersensitivity to other monoclonal antibodies; and HIV, hepatitis B or hepatitis C infection, were ineligible.

Assessment of tumor status was performed at 12 weeks, then every 6 weeks through Week 48, followed by every 12 weeks thereafter. The major efficacy outcome measures were overall survival (OS) and progression-free survival (PFS; as assessed by blinded independent

central review (BICR) using Response Evaluation Criteria in Solid Tumors [RECIST v1.1]). Additional efficacy outcome measures were overall response rate (ORR) and response duration. A total of 834 patients were randomized: 277 patients to the pembrolizumab 10 mg/kg every 3 weeks arm, 279 to the pembrolizumab 10 mg/kg every 2 weeks arm, and 278 to the ipilimumab arm. The study population characteristics were: median age of 62 years (range: 18 to 89 years), 60% male, 98% White, 66% had no prior systemic therapy for metastatic disease, 69% ECOG PS of 0, 80% had PD-L1 positive melanoma, 18% had PD-L1 negative melanoma, and 2% had unknown PD-L1 status using the IUO assay, 65% had M1c stage disease, 68% with normal LDH, 36% with reported BRAF mutation-positive melanoma, and 9% with a history of brain metastases. Among patients with BRAF mutation-positive melanoma, 139 (46%) were previously treated with a BRAF inhibitor. The study demonstrated statistically significant improvements in OS and PFS for patients randomized to pembrolizumab as compared to ipilimumab.

Among the 91 subjects randomized to pembrolizumab 10 mg/kg every 3 weeks with an objective response, response durations ranged from 1.4+ to 8.1+ months. Among the 94 patients randomized to pembrolizumab 10 mg/kg every 2 weeks with an objective response, response durations ranged from 1.4+ to 8.2 months.

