8 STUDY ASSESSMENTS AND PROCEDURES

8.1 EFFICACY ASSESSMENTS

The intention of the study design is to closely monitor patients with safety follow-up and disease assessments in the absence of disease progression or other study discontinuation criteria.

For the purposes of this study, patients should be re-evaluated after the first 12 weeks of treatment and then every 12 weeks. **In addition to a baseline scan, confirmatory scans will** also be obtained at least 4 weeks and no more than 14 weeks following initial documentation of partial or complete response.

Primary efficacy endpoint is best ORR defined as the proportion of all treated subjects whose best response at any time during the study following initiation of therapy is confirmed CR or confirmed PR. This will be assessed according to the RECIST v1.1.(Appendix A).

PFS, defined as the time between the first dose of study therapy and the earliest date of progression or death. Subjects who have neither progressed nor died will be censored at the last tumor assessment date for PFS. The endpoint ORR and PFS will be assessed according to the RECIST v 1.1 criteria.

Additional efficacy endpoints will include the disease control rate (DCR) defined as the percentage of patients achieving CR + PR + SD at any time during the study following initiation of therapy. This will be assessed according to RECIST v1.1 criteria. The duration of response (DOR), is defined as the time between the date that the criteria are first met for CR or PR or SD and the earliest date of progression or death.

OS, defined as the time between the first dose of study therapy and death (subjects who have not died will be censored at the most recent last-known-alive date), will also be analyzed.

The tumor assessment (TA) performed during screening will be used as a baseline for efficacy assessments. CT/MRI imaging of the chest and abdomen is required at Screening and at each TA, regardless of the location of known metastases. In addition, CT/MRI scans must be obtained of anatomic regions not covered by the chest and abdomen scans in subjects where there is clinical suspicion of deep soft tissue metastases (eg, lesions in the thigh). Such additional CT/MRIs will be required at Screening when deep soft tissue disease is known/suspected and must be consistently repeated at all TAs if a deep soft tissue lesion is identified during Screening.

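### Appendix A has no lymph-node rule and conflicts with the body text on what is measurable, what is summed and how many target lesions count, so one nodal scan can be SD or PR

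*Combined protocol and SAP*

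**What the plan says.** Section 8.1 defines the primary endpoint as best ORR, confirmed CR plus confirmed PR, and adds: "This will be assessed according to the RECIST v1.1.(Appendix A"). Appendix A is therefore the working scoring rule. On target lesions it says the following.

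- **Measurability:** one dimension is enough, with a longest diameter of at least 10 mm on spiral CT. Nodes are included: "Clinical lesions will only be considered measurable when they are superficial (e.g., skin nodules and palpable lymph nodes").
- **Sum:** the longest diameters of all target lesions are added, and the total "will be calculated and reported as the baseline sum LD".
- **CR:** "Disappearance of all target lesions".
- **PR:** "At least a 30% decrease in the sum of the LD of target lesions, taking as reference the baseline sum LD".
- **SD:** "Neither sufficient shrinkage to qualify for PR nor sufficient increase to qualify for PD".
- **Target lesions:** at most five per organ and ten in total.

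The body text differs. Section 8.1 asks for two perpendicular diameters, 10 x 10 mm on spiral CT, and describes adding the largest diameter to its perpendicular. It allows at most two target lesions per organ and five in total, and its baseline sum is of diameters with no axis named. The imaging footnote to the study calendar (Section 1.3) speaks of a sum of perpendicular diameters. No section gives a short-axis measurement, a nodal size limit or a definition of a node of normal size.

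**The concern.** A lymph node is a normal structure and may remain visible after the tumour in it has gone. A rule that adds longest diameters and asks for disappearance does not say how to score such a node. If its longest diameter has fallen by less than 30%, Appendix A scores it SD. Under another measurement that the documents also describe, the same scan can pass 30%.

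This matters because ORR is the primary endpoint, the trial is open-label and single-centre, and both decision rules are counts of responders: stop at 5 or fewer of 14, and reject the null at 21 or more of 44. The measurement rule should be settled before responses are counted.

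**Working it through.** **1. The passages side by side (spiral CT)**

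| Item | Appendix A | Section 8.1 | Study calendar footnote |
|---|---|---|---|
| Measurable | one dimension, at least 10 mm | 10 x 10 mm | – |
| Summed | longest diameter | diameters, axis not named; elsewhere largest plus perpendicular | perpendicular diameters |
| Target-lesion limit | 5 per organ, 10 total | 2 per organ, 5 total | – |
| Nodal rule | none | none | none |

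Appendix A is titled RECIST 1.1 and Section 8.1 says it applies RECIST v1.1. They set different limits, so they cannot both state the same criteria correctly.

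**2. Effect on one node**

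The sizes are assumed for illustration, and the node is the only target lesion. Percent change = (follow-up − baseline) / baseline. The 30% threshold is Appendix A's. The documents give no threshold for a perpendicular sum or a short axis, so applying 30% to them is my assumption.

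| Node (mm) | Longest diameter | Perpendicular sum | Short axis |
|---|---|---|---|
| 15 x 18 to 9 x 14 | (14 − 18)/18 = −22.2%: SD | (23 − 33)/33 = −30.3%: meets 30% | (9 − 15)/15 = −40%: meets 30% |
| 15 x 20 to 11 x 14 | (14 − 20)/20 = −30.0%: PR | (25 − 35)/35 = −28.6%: below 30% | (11 − 15)/15 = −26.7%: below 30% |

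In the first row Appendix A gives the less favourable category, and in the second the more favourable one.

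**3. The plan's own design figure**

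Inputs from Sections 9.1, 9.2 and 9.4.2: null ORR 35%, alternative 55%, 14 + 30 patients, continue with 6 or more of 14, reject with 21 or more of 44.

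P(reject | p) = sum over x = 6 to 14 of P[Bin(14, p) = x] × P[Bin(30, p) ≥ 21 − x].

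- p = 0.55: 0.8001, which reproduces the stated 80% power.
- p = 0.35: 0.0458, within the stated alpha of 0.05.

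The power leaves no slack.

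**4. Hypothetical sensitivity**

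- One stage-2 responder scored SD is equivalent to replacing 21 by 22 in the formula. Power at 55% is then 0.7418.
- The mirror case, one stage-2 non-responder scored PR, is equivalent to replacing 21 by 20. The type I error at 35% is then 0.0767.
- If a share m of true responders is scored SD, then p = 0.55 × (1 − m):

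| m | p | Power |
|---|---|---|
| 1% | 0.5445 | 78.2% |
| 2% | 0.5390 | 76.3% |
| 5% | 0.5225 | 69.9% |

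The share m is an assumption throughout.

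**The case against.** Several stronger readings are tempting, and the documents do not support them.

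- **A persistent node can never be CR.** Appendix A provides a route. Where residual disease is hard to tell from normal tissue, "it is recommended that the residual lesion be investigated (fine needle aspirate/biopsy) to confirm the complete response status". It also allows cytology or histology to separate PR from CR in rare cases. That route is only recommended, the study calendar schedules no biopsy for it, and it does not move a node from SD to PR.
- **Losing CR lowers ORR.** It does not. CR and PR both count, so only SD scoring reaches the 14- and 44-patient rules.
- **ORR is biased downward.** The second node in the working shows the opposite direction. The sum may also include non-nodal lesions, which dilute the nodal effect.
- **A 7 x 12 mm node could be the sole target lesion.** Appendix A's one-dimension rule would accept it, but Section 8.1's 10 x 10 mm rule would not. Appendix A also asks for cytology or histology of a solitary lesion. What remains is a conflict between the two passages.
- **The 35% benchmark was scored by a different nodal rule.** In Section 2.3.2.2 the words "using Response Evaluation Criteria in Solid Tumors [RECIST v1.1" qualify the PFS outcome. ORR is listed separately with no criteria stated, so the comparison cannot be drawn from this text.

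It is also fair to say that inclusion criterion 1 limits stage III entry to unresectable in-transit disease. Stage IV patients may have nodal targets, but how many is not stated. The absence of a nodal rule and the three internal conflicts still stand.

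**Conclusion.** The concern holds as a defect of specification. Appendix A governs the primary endpoint, treats nodes like any other lesion, and disagrees with the body text on measurability, on the quantity summed and on target-lesion limits. As a result, the same nodal scan can be SD or PR.

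The direction and size of any effect on ORR are not known. The node sizes are assumed, and the documents give no share of patients with nodal targets. The power losses (to 74.2% for one lost responder, or to 69.9% if 5% of true responders are lost) and the type I error of 7.7% in the mirror case show how sensitive the design is. They are not forecasts. The sponsor should make the correction because it decides how the primary endpoint is scored and costs little.

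**What to change.** Replace the Appendix A text with the RECIST v1.1 criteria that the protocol names, including their rules for measuring nodes, for accepting a node as a target lesion and for CR when nodes are involved. Take the numerical limits from the published criteria, because they are not in these documents. Make Section 8.1 (measurability, quantity summed, target-lesion limits) and the imaging footnote to the study calendar agree with that text. Add a field to the tumour-measurement eCRF that marks a lesion as nodal and records its short axis.

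The cost is an amendment of wording and one eCRF field. Existing scans can be re-measured, and the sample size stays at 44. A small downside is that some patients whose only lesion is a small node may no longer count as having measurable disease.
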